#### 16.3.2.3. Missing Data Methods for Correlation between CS Dose Reduction and Blood Pressure (Hypertension), Measures of Glycaemic Control, Weight, Body Habitus/Cushingoid Features, and Mood/Emotional Well-being

Missing values for correlation analysis will not be imputed and will be based on the OC approach.

### 16.3.3. ANALYSIS OF EXPLORATORY EFFICACY VARIABLES

Exploratory efficacy analyses will be based on the mITT population. P-values presented for exploratory analyses are for information purposes only.

#### 16.3.3.1. Analyses of Binary/Categorical Endpoints

The following exploratory endpoints will be analyzed with the same approach as the primary efficacy endpoint described in Section 16.1.3.

- Percent of subjects achieving a 75% or greater reduction in CS dose (prednisone or equivalent) at Week 39 from baseline
- Percent of subjects CS-free at Week 39
- Percent of subjects achieving a dose of CS of less than or equal to 7.5 mg per day of prednisone (or equivalent) at Week 39

Document: CCI

Author: PPD

Version Number:

Version Date:

Final 2.0  
12Apr2019

Template No: CCI

Effective Date: 01Apr2016

Reference: CCI

Copyright © 2009, 2010, 2012, 2016 CCI. All rights reserved.

The contents of this document are confidential and proprietary to CCI. Unauthorized use, disclosure or reproduction is strictly prohibited.

## Analysis Plan

- Percent of subjects with fasting glucose less than or equal to 125 mg/dL at Week 39
- Percent of subjects experiencing MC or episode of MG worsening requiring inpatient care from baseline through Week 39
- Percent of subjects experiencing MC or episode of MG worsening requiring inpatient care from Week 39 to Week 45
- Percent of subjects with 0, 1, or 2 episodes of MG worsening from baseline to Week 39

In the case of sparse events, where at least one of the frequencies is less than 5 in a given cell (i.e., a unique combination of baseline CS dose level, treatment, and the binary response), both unstratified and stratified analyses will be performed using exact methods. For the unstratified analysis, the Fisher's exact test (Agresti, 1992) will be used for treatment comparison. The odds ratio and the exact 95% confidence interval will also be calculated overall and separately for each stratified baseline CS dose level (15-40 mg/day versus 41-60 mg/day). For the stratified analysis, the Zelen's exact test will be used to test homogeneity of odds ratios. The CMH common odds ratio and its exact 95% confidence interval will also be calculated. Finally, an exact test will be used to test the hypothesis of the common odds ratio being 1.

## 16.3.3.2. Analysis of CFB Values

The following exploratory endpoints will be analyzed using ANCOVA model similar to the secondary endpoint in Section 16.2.3.1.

- CFB in fasting serum glucose (mg/dL) at Week 39
- CFB in MG-QOL 15 at Week 39 and Week 45
- CFB in MG-ADL at Week 39 and Week 45
- CFB in QMG Total Score at Week 39, Week 42 and Week 45
- CFB in MG Composite at Week 39, Week 42 and Week 45
- CFB in serum IgG Trough at Week 9, Week 24, and Week 39
- CFB in binding, blocking, and modulating AChR antibodies at Week 39
- CFB in HbA1c (%) at Week 39

The ANCOVA model will include CFB value as dependent variable, treatment and baseline daily CS dose level (categorical variable) as fixed factors, and baseline assessment value as covariates. Both the LOCF and OC approaches will be used to handle missing data. Treatment comparison will also be performed using the MMRM model described in Section 16.3.2.2.

Document: CCI

Author: PPD

Version Number:

Final 2.0

Version Date:

12Apr2019

Template No: CCI

Reference: CCI

Effective Date: 01Apr2016

Copyright © 2009, 2010, 2012, 2016 CCI. All rights reserved.

The contents of this document are confidential and proprietary to CCI. Unauthorized use, disclosure or reproduction is strictly prohibited.

## Analysis Plan

**16.3.3.3. Analysis of Correlation between CS Dose Reduction and Blood Pressure (Hypertension), Measures of Glycaemic Control, Weight, Body Habitus/Cushingoid Features, and Mood/Emotional Well-being at Week 39**

The correlation between the percent reduction in daily CS dose (%) at Week 39 and each of the variables specified in Section 16.3.1.16 will be explored.

The Pearson correlation coefficient (Conover, 1998) will be calculated for continuous variables including CFB in blood pressure, fasting serum glucose, HbA1c, body weight, and the total score of WHO-5.

For body habitus/cushingoid features, the results will be mapped to the ordinal scale, as follows:

Absent = 0; mild = 1; moderate = 2; severe = 3

CFB will then be derived based on these mapped ordinal values, and the Pearson correlation coefficient between percent CS dose reduction and CFB in each body habitus/cushingoid feature will be calculated.

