3.7.3 WHO-Five (WHO-5) Well-Being Index

The WHO-5 Well-Being Index score will be used to measure CS side effects. This index is an easy to use 5-item questionnaire designed to measure current mental well-being (over the last 2 weeks) and may be a useful tool for reflecting mood (48,49,50,51). Cross cultural evaluation has been performed and the index has been utilized in clinical trials.

The WHO-5 Well-Being Index and scoring is provided in Appendix 9.

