5.1.3.3 Exploratory Efficacy Analyses

Exploratory efficacy analyses will be based on the ITT population. The following exploratory efficacy variables will be analyzed with the same approach as the primary efficacy endpoint using the ITT population: In the situation where the CMH method is not appropriate due to the sparse events, the Fisher exact test will be used for treatment comparison.

Exploratory efficacy variables that will be evaluated in this study include the following:

- Percent of subjects achieving a 75% or greater reduction in CS dose (prednisone or equivalent) at Week 39 (Visit 14) from Baseline/Week 0 (Visit 1)
- Percent of subjects CS-free at Week 39 (Visit 14)
- Percent of subjects achieving a dose of CS of less than or equal to 7.5 mg per day of prednisone (or equivalent) at Week 39 (Visit 14)
- Percent of subjects with fasting glucose less than or equal to 125 mg/dL at Week 39 (Visit 14)
- Percent of subjects experiencing MC (as defined in Section 3.3.5) or episode of MG worsening requiring inpatient care from Baseline/Week 0 (Visit 1) through Week 39 (Visit 14)
- Percent of subjects experiencing MC or episode of MG worsening requiring inpatient care from Week 39 to Week 45 (at Visit 14 and Visit 16)
- Percent of subjects with 0, 1, or 2 episodes of MG worsening from Baseline/Week 0 to Week 39 (Visit 1 to Visit 14) (in aggregate and by number of episodes/subject).

The following exploratory endpoints will be analyzed using the ANCOVA with treatment as main factor and baseline CS dose as covariate. In addition, the mixed model for repeated measurement (MMRM) will also be performed.

- Change from Baseline/Week 0 in fasting serum glucose at Week 39 (Visit 14)
- Change in 15-Item MG-QOL 15 from Baseline/Week 0 to Week 39 (Visit 1 to Visit 14), and from Baseline to Week 42 and Week 45 (Visit 15 and Visit 16)
- Change in MG-ADL from Baseline/Week 0 to Week 39 (Visit 14), and from Baseline to Week 42 and Week 45 (Visit 15 and Visit 16)
- Change from baseline in serum IgG trough at Week 9 (Visit 4), Week 24 (Visit 9), and Week 39 (Visit 14)
- Change from baseline in binding, blocking, and modulating AChR antibodies at Week 39 (Visit 14)
- Change from baseline in HbA1c at Week 39 (Visit 14)

In addition, exploratory analyses of the correlation between CS dose reduction and blood pressure (hypertension), measures of glycemic control, weight, body habitus/Cushingoid features, and mood/emotional well-being will be explored.

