## 7. STATISTICAL CONSIDERATIONS

### 7.1. ADJUSTMENTS FOR COVARIATES AND FACTORS TO BE INCLUDED IN ANALYSES

The following covariates and factors are used in the analyses. For details of their inclusion in the models, see the specific analysis section.

- Baseline daily CS dose (prednisone or equivalent) level (15-40 mg, 41-60 mg); as a categorical variable
- Baseline value
- Treatment group (IGIV-C, Placebo)
- Protocol specified visits (Week 0, Week 3, Week 6, Week 9, Week 12, Week 15, Week 18, Week 21, Week 24, Week 27, Week 30, Week 33, Week 36, Week 39, Week 42, Week 45)
- Treatment-by-visit interaction

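### SAP 16.3.3.3 does not say how treatment arm enters the correlations with CS reduction; a coefficient across both arms would mix in any direct IGIV-C effect, most plausibly on WHO-5

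*SAP*

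**What the plan says.** Protocol 5.1.3.3 announces "exploratory analyses of the correlation between CS dose reduction and blood pressure (hypertension), measures of glycemic control, weight, body habitus/Cushingoid features, and mood/emotional well-being". SAP 16.3.3.3 implements this as "The correlation between the percent reduction in daily CS dose (%) at Week 39 and each of the variables specified in Section 16.3.1.16". For the continuous measures it states: "The Pearson correlation coefficient (Conover, 1998) will be calculated for continuous variables including CFB in blood pressure, fasting serum glucose, HbA1c, body weight"; the WHO-5 total score is in the same list. For the Cushingoid items, graded 0 to 3, "the Pearson correlation coefficient between percent CS dose reduction and CFB in each body habitus/cushingoid feature will be calculated".

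SAP 16.3.3.3 mentions no treatment term, partial correlation or by-arm calculation. SAP 7.1 lists treatment group among the factors but leaves its use to each section: "For details of their inclusion in the models, see the specific analysis section". The neighbouring change-from-baseline analysis (SAP 16.3.3.2) does use it: "The ANCOVA model will include CFB value as dependent variable, treatment and baseline daily CS dose level (categorical variable) as fixed factors". SAP 16.3.3.4 asks for subgroup summaries by treatment.

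The correlations use the mITT population (SAP 16.3.3) and observed cases only (SAP 16.3.2.3). Exploratory p-values are for information only.

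**The concern.** The trial is designed on the expectation that treatment drives CS reduction, with 70% against 30% responders. If treatment also moves the second variable by a route other than steroid reduction, a coefficient taken over both arms contains the product of the two arm differences as well as the association among similarly treated subjects.

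WHO-5 is the clearest case. Protocol 3.7.3 says "The WHO-5 Well-Being Index score will be used to measure CS side effects", yet the instrument measures current mental well-being. Protocol 1.2 describes IVIg as improving MG symptoms in about 70% of patients, so better MG control could raise WHO-5 directly. A positive all-subject correlation could then be read as a benefit of less steroid when part or all of it is a benefit of IGIV-C. What is at stake is the interpretation of an exploratory result.

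**Working it through.** **Plan's own figure.** The documents give no figure for the correlations, so the sample size is reproduced to fix n. With 70% v 30%, two-sided 0.05, 80% power and pooled variance:

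n per arm = [1.96·√(2·0.5·0.5) + 0.8416·√(0.21 + 0.21)]² / 0.40² = (1.386 + 0.545)² / 0.16 = 23.3, rounded up to 24.

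Allowing for 20% discontinuation, 48/0.8 = 60 randomized. Both figures match Protocol 5.2. About 48 subjects, or 24 per arm, would then have Week 39 data.

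**Formula.** Take two equal arms (1:1 allocation) with unit within-arm SD. Let r_w be the within-arm correlation, and let dx and dy be the arm differences in CS reduction and in the second variable. Greater reduction and higher WHO-5 are both scored positive. The all-subject coefficient is

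r = (r_w + dx·dy/4) / √[(1 + dx²/4)(1 + dy²/4)].

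**Inputs.** If percent reduction is normal within arms, 70% v 30% implies dx = z(0.70) − z(0.30) = 1.05 SD. A slightly smaller range, 0.8 to 1.0, is assumed here. The documents give no value for dy; 0.5 to 0.8 SD for WHO-5 is an assumption, shown beside dy = 0.

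| dx | dy | all-subject r if r_w = 0 | all-subject r if r_w = 0.20 |
|---|---|---|---|
| 0.8 | 0 | 0 | 0.20/√1.16 = 0.19 |
| 1.0 | 0 | 0 | 0.20/√1.25 = 0.18 |
| 0.8 | 0.5 | 0.10/√(1.16·1.0625) = 0.09 | 0.30/1.110 = 0.27 |
| 1.0 | 0.8 | 0.20/√(1.25·1.16) = 0.17 | 0.40/1.204 = 0.33 |

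**Simulation.** This used 20,000 trials per case at N = 48 with dx = 1.05 and r_w = 0. A nominal 5% test of the all-subject coefficient is significant in 11.8% of trials at dy = 0.5 and 22.5% at dy = 0.8. The partial correlation adjusted for arm stays at 5% in both. With r_w = 0.30 and dy = 0, the all-subject mean is about 0.26 and is detected in 45.6% of trials; the adjusted mean is about 0.30, detected in 55%.

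**By-arm alternative.** On the Fisher z scale, 24 subjects give a 95% half-width of 1.96/√21 = 0.43, or about ±0.40 in r around zero. A partial correlation on 48 subjects with two adjustment terms gives 1.96/√43 = 0.30, or about ±0.29.

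**The case against.** The SAP never says that the arms are pooled. The output conventions in SAP Appendix 1 say that totals across treatment groups are in general not presented after randomization. These are Week 39 outputs, and SAP section 8 leaves layout to templates not included in the documents. On that reading the coefficients may appear by arm, which removes the between-arm artefact. This objection largely stands: pooling is one reading of a silent text. The convention is qualified as general and concerns presentation, however, and by-arm coefficients at about 24 subjects are imprecise.

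Three stronger readings are tempting, and the documents do not support them.

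- A reader might infer that large infusion volumes let IGIV-C act on blood pressure and weight. Placebo is given at equal volumes (Protocol 3.1), and Week 39 is a visit without infusion.
- A reader might infer that the coefficient could hide a true association or point the wrong way. That needs a direct effect opposing the steroid effect, and the documents describe no such route. For WHO-5, better MG control and less steroid would push in the same direction, so the expected distortion is inflation.
- A reader might infer that this is the only analysis bearing on clinical benefit. The SAP also compares the arms on fasting glucose and HbA1c with treatment in the model (16.3.3.2) and on the 125 mg/dL glucose threshold (16.3.3.1). It summarises Cushingoid features and WHO-5 by treatment and visit (17.4, 17.5).

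It is also fair to say that adjusting for arm does not isolate a steroid effect. Under Protocol 3.3.3 the CS dose is raised when QMG worsens, so MG control can affect both CS reduction and well-being within each arm.

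**Conclusion.** The omission is real and minor. SAP 16.3.3.3 does not state how treatment enters, and an all-subject Pearson coefficient would absorb any direct IGIV-C effect on the second variable. Under the assumed shifts, an absent association looks like r = 0.09 to 0.17 and a true +0.20 is overstated at 0.27 to 0.33. With no direct effect nothing spurious arises, only attenuation to 0.18 or 0.19 from 0.20.

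The sizes rest on the assumed WHO-5 shift, normal within-arm distributions and calculation over both arms. The analysis is exploratory, in a proof-of-concept study without multiplicity control (SAP 7.4), and no primary or secondary conclusion depends on it.

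**What to change.** In SAP 16.3.3.3, make the main estimate the partial correlation between percent CS reduction and each change score, adjusted for treatment group and baseline CS dose level. Report the within-arm coefficients alongside. The unadjusted coefficient may be kept if it is labelled as such. Add a sentence that the association is exploratory and not causal, because MG control can confound it within arm.

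This takes a few lines of text and a small change to the correlation program, and costs one or two degrees of freedom. It needs no new data and leaves the sample size and primary analysis as they are.

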**16.3.3.4. Subgroup Analysis of Primary Efficacy Variable**

The primary efficacy variable of the percent of subjects achieving a 50% or greater reduction in CS dose (prednisone or equivalent) at Week 39 from Baseline will be summarized by treatment and by each of the subgroups defined in Section 7.5. Both the WOCF/LOCF and the OC approaches for handling missing data will be used. Only summary statistics will be presented without any statistical testing.

**17. SAFETY OUTCOMES**

All outputs for safety outcomes will be based on the Safety population.

There will be no statistical comparisons between the treatment groups for safety data, unless otherwise specified within the relevant section.

**17.1. ADVERSE EVENTS**

Adverse Events (AEs) will be coded using MedDRA central coding dictionary, Version 17.1.

Treatment emergent adverse events (TEAEs) are defined as AEs that started on or after the beginning of the first infusion of study medication and prior to the final study visit.

See Appendix 2 for handling of partial or missing dates/times for AEs. In the case where it is not possible to define an AE as treatment emergent or not, the AE will be classified by the worst case; i.e. treatment emergent.

Listings will include TEAEs and Non-TEAEs. Subjects with deaths, serious adverse events (SAEs), suspected adverse drug reactions (ADRs) and AEs leading to premature discontinuation from the study will be listed.

An overall summary of number of subjects and number of events within categories of interest will be provided as specified in the templates.

Document: CCI

Author: PPD

Version Number:

Version Date:

Final 2.0  
12Apr2019

Template No: CCI

Effective Date: 01Apr2016

Reference: CCI

Copyright © 2009, 2010, 2012, 2016 CCI. All rights reserved.

The contents of this document are confidential and proprietary to CCI. Unauthorized use, disclosure or reproduction is strictly prohibited.

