4.3.1 Adverse Events

AEs (includes suspected ADRs) occurring at any time between signature of the subject's ICF and the last day of the subject's participation in the clinical trial will be reported and recorded on the appropriate subject's eCRF entry.

It is the investigator's responsibility to ensure that all AEs are appropriately recorded.

AEs will be elicited by spontaneous reporting by the study individual or by a non-leading inquiry or direct observation by the study staff.

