4.4.1 Adverse Event

An AE is defined as any untoward medical occurrence in a patient or clinical investigation subject administered a medicinal product or study treatment and which does not necessarily

have a causal relationship with this administration. An AE can therefore be any unfavorable and unintended sign (including any abnormal laboratory finding, for example), symptom or disease temporally associated with the use of a medicinal product, whether or not considered related to the medicinal product.

Any AE that occurs at any time between the signature of the ICF and last day of the subject's participation in the clinical trial must be reported and recorded on the AE eCRF entry.

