For any subject, all AEs that occur at any time, between the beginning of the first infusion of IGIV-C and the final visit of the clinical trial, will be considered TEAEs.

AEs occurring during the actual IP infusions (i.e., from the initiation of the IP infusion on the first day to the completion of the total dosage of IP on the last day) and within 72 hours following the completion of the infusion of the total dosage of IP on the last day, regardless of other factors that may impact a possible causal association with product administration, will be defined as infusional AEs (i.e., an AE temporally associated with an infusion of the IP) and labeled infusional TEAEs (a subset of TEAEs).

For AEs that occur during infusions, the infusion rate in effect at the time of onset of the AE, the time of onset of the AE and the time of AE change materially in intensity and/or resolves will be captured.

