5.1.4 Safety Analyses

The safety analysis will be based on safety population.

The safety analyses will be addressed by listing and tabulation of AEs (includes suspected ADRs), vital signs, physical assessments and clinical laboratory tests. Data will be described using descriptive analyses.

Adverse events:

Safety analysis will be primarily focused on a descriptive analysis of suspected ADRs. Safety assessment will be based on the prevalence of suspected ADRs that occurred during the clinical trial.

AEs will be coded and classified using MedDRA terms (system organ class and preferred terms).

AEs will be classified as TEAEs or non-TEAEs depending on the comparison of AE onset date/time with the start date/time of study treatment with the IP. A TEAE will be defined as an AE which occurs between the beginning of the first infusion of IGIV-C and the final visit of the clinical trial. A non-TEAE will be defined as an AE which occurs prior to the first dose of IP. Non-TEAEs and TEAEs will be summarized separately.

All AEs will be summarized by presenting subject incidences and percentages, and they will also be listed by body systems with subject identification codes.

In addition, TEAEs, including suspected ADRs, will be summarized, system organ class, preferred term, causal-relationship, intensity (severity) and seriousness (serious vs.

non-serious) using descriptive statistics. At each level of summarization, a subject will only be counted once per system organ class or preferred term using the most severe or causal relationship AE.

AEs temporally associated with the infusion of the IP (i.e., infusional AEs, including infusional suspected ADRs), will be summarized by presenting infusion/subject incidences and percentage and listed. In addition, the infusion rate in effect at the time of onset of the AE, the time the AE is first reported and the time the AE changes materially in intensity and/or resolves will be also reported and listed.

Subjects with deaths, SAEs, suspected ADRs and AEs leading to premature discontinuation from the study will be listed and presented in a narrative form.

AEs for which the investigator causality assessment is missing or undetermined will be individually listed.

Vital signs:

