### 7.3. MISSING DATA

Imputation for missing values will be applied to continuous efficacy endpoints using the LOCF or the WOCF method.

Primary efficacy endpoint of CS dose:

For the primary efficacy endpoint of CS dose, the WOCF method will be applied to subjects who discontinued early from the study with adverse outcomes related to MG, defined as those subjects who met ALL criteria below:

- The primary reason for discontinuation is one of the following: “Adverse Event”, “Death”, “Discontinuation due to MG crisis requiring hospitalization”, or “MG worsening (CS-unresponsive or 2nd episode)”
- The subject had at least one adverse event (AE) with preferred term (PT) of either “Myasthenia gravis crisis” or “Myasthenia gravis”
- The AE is serious, with the reason for seriousness being “Required/Prolonged Hospitalization” or “Resulted in Death”
- The onset date/time of the AE is on or after the start date/time of the first infusion of study medication, i.e., the AE is treatment-emergent

For these subjects, the worst values, i.e., the highest average daily CS dose available among all eligible visits [including the Baseline visit, all post-baseline scheduled visits, and the Early Termination visit(s)], will be carried forward to impute the missing CS dose for all remaining visits.

For subjects who discontinued the study early due to any other reasons, the LOCF method will be used to impute the missing values, i.e., the last non-missing post-baseline CS dose value available among all eligible visits [including all post-baseline scheduled visits and the Early Termination visit(s)] will be carried forward to impute missing values for all remaining visits.

Note for the primary efficacy endpoint of CS dose, the values to be considered as candidates for carrying forward are the derived average daily CS dose at the relevant scheduled visits, incorporating potential changes in the prescribed CS dose within the prior 3 weeks (see section 16.1.1 for derivation details).

Other continuous efficacy variables:

For all other continuous efficacy variables and for all subjects who discontinued the study early, regardless of the reason, the LOCF method will be used to impute the missing values, i.e., the last non-missing post-baseline value (including scheduled, unscheduled, and early termination) will be carried forward to impute missing values for all remaining visits.

All continuous efficacy variables:

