#### 17.1.5. INFUSIONAL ADVERSE EVENTS

Infusional AEs, including infusional suspected ADRs, are those temporally associated with the infusion of the IP and are defined as TEAEs that occur from the initiation of the IP infusion and within 72 hours following the completion of the infusion of the total dosage of IP. These will be summarized by presenting infusional events and subject incidences and percentage. A corresponding listing will also be presented. In addition, the infusion rate in effect at the time of onset of the AE, the time the AE is first reported, and the time the AE changes materially in intensity and/or resolves will be also reported and listed.

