**ALGORITHM FOR TREATMENT EMERGENCE OF ADVERSE EVENTS:**

AE START DATE TIME	STUDY MEDICATION START DATE TIME	ACTION
Known	Known	If start date/time < study med start date/time, then not TEAE If start date/time >= study med start date/time, then TEAE
Partial or Missing	Known	If start date < study med start date, then not TEAE If start date > study med start date, then TEAE If start date = study med start date, then impute AE start time to the latest possible time (i.e. 23:59 if hours and minutes are missing, or 59 minutes past the hour if only minutes are missing). If this imputed date/time is after AE stop date/time, then use AE stop date/time as the imputed AE start date/time. Then: If imputed start date/time < study med start date/time, then not TEAE If imputed start date/time >= study med start date/time, then TEAE
Known	Partial or Missing	If start date < study med start date, then not TEAE If start date > study med start date, then TEAE If start date = study med start date, then impute study med start time as the earliest possible time (i.e. 00:00 if hours and minutes are missing, or 00 minutes past the hour if only minutes are missing). Then: If start date/time < imputed study med start date/time, then not TEAE If start date/time >= imputed study med start date/time, then TEAE

Document: CCI

Author: PPD

Version Number:

Version Date:

Final 2.0  
12Apr2019

Template No: CCI

Effective Date: 01Apr2016

Reference: CCI

Copyright © 2009, 2010, 2012, 2016 CCI. All rights reserved.

The contents of this document are confidential and proprietary to CCI. Unauthorized use, disclosure or reproduction is strictly prohibited.

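### SAP 17.1 ends the TEAE window before the final study visit while SAP Appendix 2 sets no end; the two need one inclusive end date that also covers early leavers

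*SAP*

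**What the plan says.** SAP 17.1 defines TEAEs as AEs that "started on or after the beginning of the first infusion of study medication and prior to the final study visit". It refers to Appendix 2 for partial or missing dates and times.

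Appendix 2 also has a row for the case where both dates are fully known. That row reads "If start date/time >= study med start date/time, then TEAE" and sets no upper limit. SAP 7.3 (the rule for carrying the worst dose forward) and SAP 16.3.1.6 likewise treat the lower bound as sufficient: 7.3 asks for an onset "on or after the start date/time of the first infusion of study medication, i.e., the AE is treatment-emergent".

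The protocol's window in 4.4.3 is "all AEs that occur at any time, between the beginning of the first infusion of IGIV-C and the final visit of the clinical trial", and 5.1.4 repeats it in substance. Collection is wider: under 4.3.1, AEs arising between consent and "the last day of the subject's participation in the clinical trial will be reported and recorded", and 4.4.1 says the same. Protocol 5.1.4 adds: "A non-TEAE will be defined as an AE which occurs prior to the first dose of IP".

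Infusional AEs in SAP 17.1.5 "are defined as TEAEs that occur from the initiation of the IP infusion and within 72 hours" of the end of the dosage, so they inherit whatever limit 17.1 sets. SAP 3.3, which lists changes from the protocol, does not mention the TEAE window.

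**The concern.** The upper bound in 17.1 is strict, so an AE whose onset is the final visit day fails it. An abnormal laboratory or examination result at Week 45 would be affected if its onset is recorded as the visit date.

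The less clear case is the early leaver. Return visits are requested only of subjects who are willing (Protocol 3.11), and SAP 16.1.1 foresees a subject who withdraws and attends no early termination visit. The SAP does not say what the final study visit is for that subject. If it is the last visit attended, an event in the days after the last infusion is outside the window. It is not a non-TEAE either, because that class is confined to onsets before the first dose.

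Safety reporting here is descriptive, with no between-group testing planned (SAP 17), so the tables are the safety result. Two programmers following 17.1 and Appendix 2 respectively could produce different tables from the same data. Any loss would fall on events close to the end of participation.

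**Working it through.** The plan gives no figure on this point to reproduce. The check is to apply the competing rules to the same onset days. Day 1 is the day of first infusion (SAP 6.1) and F is the day of the final study visit.

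- Rule A, SAP 17.1 taken literally: 1 ≤ onset < F.
- Rule B, Protocol 4.4.3 and 5.1.4, with the word between read inclusively (an assumption): 1 ≤ onset ≤ F.
- Rule C, SAP Appendix 2, known dates: onset ≥ 1.

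**Completer.** Week 45 is nominally Day 45 × 7 + 1 = 316 (visits may shift by 3 days). Rule A covers Days 1 to 315 and Rule B Days 1 to 316. The strict bound removes one day: 1/316 = 0.3% of onset days.

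**Early leaver who returns (illustrative).** Assume the last infusion is at Week 12, Day 12 × 7 + 1 = 85, and the Early Discontinuation Visit is on Day 95. The two follow-up visits, 6 and 9 weeks after the last infusion, fall on Days 85 + 42 = 127 and 85 + 63 = 148.

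| Case | Onset day | Rule A | Rule B | Rule C |
|---|---|---|---|---|
| Completer, F = 316 | 310 | TEAE | TEAE | TEAE |
| Completer, F = 316 | 316 | no | TEAE | TEAE |
| Completer, F = 316 | 317 | no | no | TEAE |
| Early leaver, F = 148 | 95 or 100 | TEAE | TEAE | TEAE |
| Early leaver, F = 148 | 148 | no | TEAE | TEAE |
| Early leaver, F = 95 | 90 | TEAE | TEAE | TEAE |
| Early leaver, F = 95 | 95 | no | TEAE | TEAE |
| Early leaver, F = 95 | 100 | no | no | TEAE |

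**Early leaver who does not return (illustrative).** Suppose the last visit attended is the Day 85 infusion and that visit counts as final. Rule A then covers Days 1 to 84. The 72 hours after the infusion run from Day 85 into Day 88, wholly outside. SAP 14.1 nevertheless credits exposure of (85 − 1 + 21)/7 = 15 weeks, or 105 days. So 105 − 84 = 21 days enter the denominator of the per-week event rate in SAP 17.1.1 with no event able to enter the numerator. If Visit 1 is the only visit, F = 1 and the condition 1 ≤ onset < 1 cannot be met.

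In the same subject, a serious MG event with hospitalization after Day 85 would be treatment-emergent under SAP 7.3 and 16.3.1.6, but would be missing from the serious-TEAE summary in 17.1.3 under Rule A.

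If the final study visit means Week 45 for everyone, a subject who never reaches Week 45 loses nothing. The documents do not settle which meaning applies.

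**The case against.** The case for leaving this alone has several parts, and most of them limit the point without removing it.

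- A reader might infer that anything found at Week 45 or at the Early Discontinuation Visit is lost. It is not: the rule acts on onset. An AE that began on Day 310 and was found at Week 45 is a TEAE under all three rules.
- The Early Discontinuation Visit is not the last visit when the two follow-up visits are attended, as Protocol 3.8.2.6 and 3.11 and SAP 6.4 ask.
- A reader might infer that the events vanish from every TEAE table. That is not established. If Appendix 2 is what gets programmed, they are counted. Yet 17.1 sends only partial or missing dates to that appendix, so its own sentence appears to govern complete dates. Its worst-case rule applies only where status cannot be determined.
- Protocol 3.8.2.6 applies the label of final study visit to Week 45 alone, so the last-visit-attended reading is a possibility and not the stated rule.
- The cut-off at the final visit is in Protocol 4.4.3 and 5.1.4. For onsets after that visit the SAP inherits the limit. Only the exclusion of the visit day itself is new.
- Deaths, SAEs and AEs leading to discontinuation are listed, and the protocol requires narratives, so a grave late event would be visible.
- For completers the infusional tables are unaffected: the last infusion is at Week 36, Day 36 × 7 + 1 = 253, and its 72 hours run into Day 256, well before Day 316.

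What remains is a contradiction between two parts of the SAP, an undefined term for early leavers, and a class of post-dose events with no category.

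**Conclusion.** The point holds as an inconsistency in definition that should be corrected before the safety tables are programmed. For completers its reach is one onset day of 316. For early leavers it depends on two things the documents leave open: what the final study visit means for them, and whether 17.1 or Appendix 2 is programmed. On the least favorable combination, all onsets from the last attended visit onward are excluded in subjects who do not return, including that infusion's 72-hour window.

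The number of events affected cannot be computed. A reader might take the planned 20% discontinuation, 0.20 × 60 = 12 subjects, as the number affected. It is the planned number of early leavers, not the number who leave without a later visit and then have an AE. Nor does Week 45 being one of four scheduled post-baseline laboratory and full-examination visits (Weeks 9, 24, 39 and 45) measure the loss. It counts occasions for detection and matters only for findings whose onset is dated to the visit.

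**What to change.** In SAP 17.1, define a TEAE as an AE with onset at or after the start of the first infusion and up to and including the subject's last day of participation. For subjects who leave without returning, count every recorded AE with onset at or after the first infusion. Put the same end of window into Appendix 2, which now has none, so that the two sections agree, and apply it throughout 17.1.1 to 17.1.5. Since this also extends the window in Protocol 4.4.3 and 5.1.4, record it in SAP 3.3.

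The cost is a few lines of SAP text and a matching change in programming. No new data are needed. The downside is that AE counts may rise slightly.
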